6.1.2 ADMINISTRATION AND/OR DOSING

Tracking Dosage: Attendance forms are completed at each site for each round. As surveys are anonymous, tracking number of sessions for each individual will require linking feedback surveys using participants’ secret code. Should secret codes not be possible to match across session, dosage will be calculated for each round based on % overall attendance.

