6.4 STUDY INTERVENTION/EXPERIMENTAL MANIPULATION ADHERENCE

Session participation will be monitored through sign in sheets at each session as well as survey completion at baseline and end of programming. Completion of the sessions and the surveys will be monitored through REDcap. Retention is facilitated by collecting detailed contact information and offering incentives for survey completion.

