8 STUDY ASSESSMENTS AND PROCEDURES

8.1 ENDPOINT AND OTHER NON-SAFETY ASSESSMENTS

Assent and Consent

Youth ages 13-17 receive a description about the research study and parental letter about the study from the community sites. The parent letter includes an option for parents/caregiver to decline their child's participation. We received a waiver of parental permission and waiver of signed consent from the University of Pittsburgh Human Subjects Research Protection Office. Research assistants review the verbal consent form with youth at the beginning of the first session and answer any questions pertaining to confidentiality, the program flow, and survey time points. The consent form covers all research surveys over the course of the program. An additional consent is used for the optional interview portion at the end of the project.

Data Collection

There are several points of data collection throughout the study including baseline surveys, feedback forms, End of Program (EOP) survey, and interview. The surveys are all anonymous, linked by a personal secret code that youth create by answering a series of questions that only they know the answer to at the beginning of each survey. This method of using a personal study code was selected to ensure anonymity and increase the likelihood of honest responses. In addition to survey data, other sources of data for this study (primarily for process evaluation and assessing intervention fidelity) include: 1) feedback forms completed by youth after the end of each session; 2) fidelity forms completed by research assistants at each session; 3) interviews with site leads and facilitators; 4) interviews with youth.

Main Study Phase

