Baseline survey: Youth are asked to complete the baseline survey the first time they attend a session (can enter study at Sessions 1 – 3; if participant is interested in joining after session 3, they are asked to return for the next round). All sites conduct web-based surveys (back up paper surveys are used as needed) on tablets using REDCap, an online data management and survey system. Responses to the anonymous web-based secure survey are entered by the youth participants themselves on an electronic tablet; no data are stored on the computers themselves. Only research staff who have been added to the project can access this online database. Data are downloaded and stored on a password-protected share drive that can only be accessed by users with the appropriate permissions. No names are connected to the survey data as each participant creates their own secret code as described above.

End of program survey: At the end of the program, youth are asked to complete an end of program survey that asks about which sessions they attended, their impressions of the program, and reassesses measures collected on the baseline survey. Surveys are self- administered on electronic tablets provided by the research staff (back up paper surveys will be used if tablets are not available or fail). All participants, regardless of the amount of curricular content completed, are eligible to take this survey; participants are asked to complete the end of program survey later if they miss the last session.

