Baseline and follow-up survey participation coincide with the beginning of the intervention and end of the program (EOP). All sites conduct web-based surveys (back up paper surveys are used as needed) on tablets using REDCap, an online data management and survey system. Youth provide detailed contact information at baseline to facilitate follow up. Contact information is confirmed again at sessions following the baseline survey. Responses to the anonymous web-based secure survey are entered by the youth participants themselves on an electronic tablet; no data are stored on the computers themselves.

Only research staff who have been added to the project can access this online database. Data are downloaded and stored on a password-protected share drive that can only be accessed by users with the appropriate permissions. No names are connected to the survey data as each participant creates their own secret code as described above. The only study documents that contain unique personal identifiers are contact forms and the contact list of participants (youth and prevention educators) that are kept to assist with re-contacting participants for follow up surveys. Contact forms are stored in a secure file drawer inside the locked office of the PI whenever not in use. Contact forms are stored separately from any survey data collected in this study (the survey data are collected via computer and immediately housed in a password-protected secure database). The names of participants are kept in encrypted files on a password-protected server behind the UPMC firewall.

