9.4.5 BASELINE DESCRIPTIVE STATISTICS

Summary statistics, including frequency tables, percentages, and proportions, will be used to describe participant demographic data and social network characteristics. Histograms, boxplots, quantile-quantile plots, and quantile-normal plots will be generated to visualize distribution functions and assess normality of quantitative data. Moreover, measures of center (mean, median) and measures of spread (standard deviation, range, interquartile range) will be calculated and presented. To assess differences at baseline between the youth in the experimental and control groups, demographics such as grade-level, race, and parental education will be compared while accounting for within-neighborhood clustering. Demographic variables resulting in between-arm imbalances will be considered as covariates in the primary and secondary analyses.

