10.1.9 DATA HANDLING AND RECORD KEEPING

10.1.9.1 DATA COLLECTION AND MANAGEMENT RESPONSIBILITIES

Data collection will be the responsibility of the clinical trial staff at the site under the supervision of the site investigator. The investigator will be responsible for ensuring the accuracy, completeness, legibility, and timeliness of the data reported.

All source documents will be completed in a neat, legible manner to ensure accurate interpretation of data.

Hardcopies of the contact sheets, attendance sheets, and fidelity forms will be provided for use as source document worksheets for recording data. Data recorded in the electronic database derived from source documents will be consistent with the data recorded on the source documents.

The main survey data are entered directly by study participants via an electronic notepad displaying an online survey. Those data are transmitted directly into the secure database.

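### Section 6.1.2 ties per-person session counts to code-matched anonymous feedback forms, and no section names the sign-in or attendance sheets as the source of the primary attendance endpoint

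*Combined protocol and SAP*

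**What the plan says.** Sections 1.1, 3 and 9.1 define the primary feasibility endpoint as a proportion between 0 and 1 for each participant. The numerator is the number of sessions that person attended; the youth maximum is 12. Sections 3 and 9.1 say attendance is taken at the start and finish of every session, but not on which form.

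Section 6.1.2 first mentions attendance forms, kept by site and round. It then says that, because surveys are anonymous, "tracking number of sessions for each individual will require linking feedback surveys" through the participants' codes. The stated response to failed matching is: "Should secret codes not be possible to match across session, dosage will be calculated for each round based on % overall attendance". Section 8.1 explains that youth make the code by answering "questions that only they know the answer to at the beginning of each survey", so it is entered afresh each time.

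Sheets appear in two other places. Section 6.4: "Session participation will be monitored through sign in sheets at each session as well as survey completion at baseline and end of programming". Section 10.1.9.1: "Hardcopies of the contact sheets, attendance sheets, and fidelity forms will be provided for use as source document worksheets for recording data". Neither ties the sheets to the endpoint. Section 8.1 (Data Management) adds: "The only study documents that contain unique personal identifiers are contact forms and the contact list of participants". Sign-in and attendance sheets are not on that list.

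**The concern.** The quantity that Section 6.1.2 says can be had only through code linkage is the numerator of a primary endpoint. The section says this with attendance forms already in view, so a reader could conclude that those forms are not expected to give a count per person. One youth's full count would then rest on up to 12 separate code entries agreeing. The $5 payment per feedback form (Section 5.5) encourages completion but does nothing for mismatched codes.

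Two things are at stake if an analyst follows Section 6.1.2 for the endpoint. Attended sessions may go uncounted, which pushes attendance down. Or the fallback replaces participant values with one percentage per round, although Sections 9.2, 9.3 and 9.4.2 call for within-arm 95% confidence intervals, a proportion of participants achieving the outcome, ICCs, and separate results for youth and adults. Only attendance is exposed: end-of-program satisfaction and the exploratory outcomes do not need matching from session to session.

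**Working it through.** **1. The plan's own precision figure.** Section 9.2 assumes 25 adolescents with complete data per arm and a 95% margin of error of at most 0.20 for a proportion. The Wald half-width at its maximum is 1.96 × √(0.5 × 0.5 / 25) = 0.196. The figure reproduces, ignoring clustering, and it presupposes 25 person-level values per arm.

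**2. The candidate sources side by side.**
- Section 6.1.2: feedback forms linked by code, or else a round percentage.
- Section 6.4: sign-in sheets, for monitoring participation.
- Section 10.1.9.1: attendance sheets, as source worksheets.
- Section 8.1: the end-of-program survey also asks youth which sessions they attended.
- Sections 3, 9.1 and 9.4.2: the endpoint and its analysis, with no source form named.

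Sections 2.1 and 9.1 describe tracking as something separate from surveys. Sections 6.1.1 and 7.3 have staff contacting people who miss sessions, which requires knowing who was absent. So person-level sheets are likely, but this is inference, and the Section 8.1 statement on identifiers leaves it unsettled.

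**3. Loss if linked forms are counted.** Suppose a share m of attended sessions yields a completed, matched form and the rest go uncounted. Recorded attendance is then m × true attendance. The documents give no m. With an assumed true value of 0.75:
- m = 0.95: 0.7125, or 0.71
- m = 0.90: 0.675, or 0.68
- m = 0.80: 0.60

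**4. What survives the fallback.** All youth share the denominator 12, so the mean of individual proportions equals total youth sessions attended / (12 × number of youth). For two rounds of, say, 12 and 13 youth with percentages a and b, the arm mean is (12a + 13b) / 25. The youth point estimate is therefore recoverable, provided the percentage is for youth alone. Section 6.1.2 does not say that it is, and in the intervention arm adults attend as well.

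**5. What does not survive.** Illustration, all assumed: 25 youth, 75% overall attendance, hence 0.75 × 25 × 12 = 225 attended sessions, mean 9. Each youth has at least one session, because Section 8.1 says "Youth are asked to complete the baseline survey the first time they attend a session".
- Smallest spread: everyone attends 9, SD 0.
- Largest spread: 18 attend 12, one attends 3, six attend 1 (216 + 3 + 6 = 225). Squared deviations: 18 × 9 + 36 + 6 × 64 = 582. On the proportion scale, SD = √(582 / 144 / 24) = 0.41. The 95% half-width is 2.064 × 0.41 / √25 = 0.17, clustering ignored.
- Proportion of youth attending at least 9 of 12 (an assumed cut-off; the documents give none): the minimum k satisfies 12k + 8(25 − k) ≥ 225, so k = 7, or 28%. The maximum is 25 of 25, or 100%.

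The same overall percentage fits all of these. They bound what is arithmetically possible and are not a forecast. An ICC likewise needs variation within sites, which a round percentage does not carry.

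**6. An interval from round percentages alone.** If each site runs one round (assumed), an arm has two percentages. With equal weights, the t interval on 1 df has half-width 12.706 × d / 2 for a difference d: 0.32 for 5 points, 0.64 for 10. Some interval can be formed, but not one of the precision in step 1.

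**The case against.** The strongest reply is that Section 6.1.2 is about dosage and gives survey anonymity as its reason. Anonymity blocks linking attendance to survey answers; it does not stop anyone counting names on a sheet. Section 8.1 places feedback forms mainly under process evaluation and fidelity, and has youth complete them after a session ends. That does not match an endpoint recorded at both the start and the end. With sign-in sheets, source-document attendance sheets, participant tracking and calls to absentees, the documents point to person-level attendance data. The identifier sentence in Section 8.1 stands among text on survey confidentiality and is thin evidence that the sheets are nameless.

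Most of this stands. A reader might infer that the trial has no individual attendance data, or that its primary endpoint cannot be computed. The documents do not support either. A reader might also infer that the plan scores an unmatched form as an absence. It does not say so; its only stated response to failed matching is the round percentage, so step 3 rests on a counting rule as well as on rates that the plan does not give.

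What the reply does not remove is the text itself. Section 6.1.2 states its requirement without qualification, concerns the endpoint's own numerator, and is contradicted by no sentence that names another source.

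**Conclusion.** The point holds as an unreconciled passage of modest severity. Section 6.1.2 should not govern the primary attendance endpoint, and at present nothing in the protocol says that it does not.

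If it were applied, any bias from lost sessions would be downward, by an amount the documents do not allow to be estimated; the 0.71, 0.68 and 0.60 figures depend on assumed match rates. It would be wrong to take the 0.41 SD or the 28% to 100% range as expected error: the first needs an extreme attendance pattern and the second an invented cut-off. The firm conclusion is qualitative. Under the fallback the youth mean can be recovered if youth percentages are reported separately and rounds are weighted by size. The participant-level SD and 95% CI, the proportion achieving the outcome and the attendance ICC cannot be computed, and no separate youth and adult percentages are specified.

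**What to change.** In Sections 6.1.2 and 9.1, state that the primary attendance endpoint is computed per person, separately for youth and adults, from the per-session sign-in or attendance sheets. The sheets should carry either a name or an attendance number keyed to the existing contact list, be stored apart from the survey data, and have no link to the secret code. If names are used, add the sheets to the list of identifying documents in Section 8.1. Confine code linkage and the round-level fallback to analyses that relate dose to survey answers.

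If the sheets already identify participants, as the messages to people who miss a session suggest, the cost is protocol wording, data entry and one more document to secure. If they are head counts, an identifier is needed from the first session, since head counts cannot be individualised later.

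There is one analytic cost. Section 9.4.5 says: "Demographic variables resulting in between-arm imbalances will be considered as covariates in the primary and secondary analyses". Sheet-based attendance with no link to the surveys cannot be adjusted for survey demographics; that would still need code linkage. The within-arm estimates in Sections 9.3 and 9.4.2 do not need it, and survey anonymity is unaffected.

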6.2 FIDELITY

6.2.1 INTERVENTIONIST TRAINING AND TRACKING

Facilitators at the community-partner sites will be trained on the intervention curriculum by study personnel prior to launch of the study. Pilot testing before the start of the study will allow study staff to finalize the curriculum and training necessary to begin the intervention. The facilitators that are chosen for this study have experience being facilitators in similar research studies. Research personnel will attend every session and complete fidelity feedback forms on the structure and completion of the session. Surveys will also be given to the facilitators to review their participation and program leading for the intervention. Sessions will be tracked in an online database and on the research database with session updates, upload of fidelity forms, and study tracking. Survey tracking from REDCap will be completed through the database and on REDCap.

6.3 MEASURES TO MINIMIZE BIAS: RANDOMIZATION AND BLINDING

Assignment of Interventions: Randomization was performed at the neighborhood level. The initial randomization included 4 community-based sites. The study statistician performed this randomization as a one-to-one randomization between control and intervention arms.

Randomization was performed after approval for the study was obtained for a site in a new neighborhood so that the randomization assignment would not influence a site’s willingness to participate. Sites chosen for the program have participated in other studies and interventions prior to the implementation of SCC, so many of the sites and facilitators were familiar with the content and programming guidelines. Due to the study design, investigators, research staff, participants, facilitators, and community partners could not be blinded to intervention assignment.

6.4 STUDY INTERVENTION/EXPERIMENTAL MANIPULATION ADHERENCE

Session participation will be monitored through sign in sheets at each session as well as survey completion at baseline and end of programming. Completion of the sessions and the surveys will be monitored through REDcap. Retention is facilitated by collecting detailed contact information and offering incentives for survey completion.

6.5 CONCOMITANT THERAPY

N/A

6.5.1 RESCUE THERAPY

N/A

7 STUDY INTERVENTION/EXPERIMENTAL MANIPULATION DISCONTINUATION AND PARTICIPANT DISCONTINUATION/WITHDRAWAL

7.1 DISCONTINUATION OF STUDY INTERVENTION/EXPERIMENTAL MANIPULATION

A participant may stop participating and withdraw from the study at any time. If a subject discontinues from either arm but not from the study, remaining study procedures will be completed as indicated by the study protocol.

The data to be collected at the time of study intervention discontinuation may include the reason(s) for discontinuing from the intervention, and methods for determining the need to discontinue.

7.2 PARTICIPANT DISCONTINUATION/WITHDRAWAL FROM THE STUDY

Participants are free to withdraw from participation in the study at any time upon request. An investigator may discontinue a participant from the study for the following reasons:

- Request from youth to discontinue their participation
- Lost-to-follow up; unable to contact subject (see **Section 7.3, Lost to Follow-Up**)
- Any event or medical condition or situation occurs such that continued collection of follow-up study data would not be in the best interest of the participant
- The participant meets an exclusion criterion (either newly developed or not previously recognized) that precludes further study participation

The reason for participant discontinuation or withdrawal from the study will be recorded. Subjects who withdraw from the study, before any data collection is completed, such as survey responses, documentation of consent/assent will be kept in the database.

7.3 LOST TO FOLLOW-UP

A participant will be considered lost to follow-up if they fail to respond to at least 10 contact attempts for follow-up surveys and the 3 months window for follow-up survey completion has passed.

Missing sessions (not participating in the program) will not be considered a reason for loss to follow up. We will make every attempt to reach participants who are missing sessions including using all contact information provided as well as through the community facilitators in their neighborhood.

Before a participant is deemed lost to follow-up, the investigator or research team member will make every effort to regain contact with the participant. These contact attempts will be documented in the participant's study file. Should the participant continue to be unreachable, they will be considered to have withdrawn from the study with a primary reason of lost to follow-up.

8 STUDY ASSESSMENTS AND PROCEDURES

8.1 ENDPOINT AND OTHER NON-SAFETY ASSESSMENTS

Assent and Consent

Youth ages 13-17 receive a description about the research study and parental letter about the study from the community sites. The parent letter includes an option for parents/caregiver to decline their child's participation. We received a waiver of parental permission and waiver of signed consent from the University of Pittsburgh Human Subjects Research Protection Office. Research assistants review the verbal consent form with youth at the beginning of the first session and answer any questions pertaining to confidentiality, the program flow, and survey time points. The consent form covers all research surveys over the course of the program. An additional consent is used for the optional interview portion at the end of the project.

Data Collection

There are several points of data collection throughout the study including baseline surveys, feedback forms, End of Program (EOP) survey, and interview. The surveys are all anonymous, linked by a personal secret code that youth create by answering a series of questions that only they know the answer to at the beginning of each survey. This method of using a personal study code was selected to ensure anonymity and increase the likelihood of honest responses. In addition to survey data, other sources of data for this study (primarily for process evaluation and assessing intervention fidelity) include: 1) feedback forms completed by youth after the end of each session; 2) fidelity forms completed by research assistants at each session; 3) interviews with site leads and facilitators; 4) interviews with youth.

Main Study Phase

Baseline survey: Youth are asked to complete the baseline survey the first time they attend a session (can enter study at Sessions 1 – 3; if participant is interested in joining after session 3, they are asked to return for the next round). All sites conduct web-based surveys (back up paper surveys are used as needed) on tablets using REDCap, an online data management and survey system. Responses to the anonymous web-based secure survey are entered by the youth participants themselves on an electronic tablet; no data are stored on the computers themselves. Only research staff who have been added to the project can access this online database. Data are downloaded and stored on a password-protected share drive that can only be accessed by users with the appropriate permissions. No names are connected to the survey data as each participant creates their own secret code as described above.

End of program survey: At the end of the program, youth are asked to complete an end of program survey that asks about which sessions they attended, their impressions of the program, and reassesses measures collected on the baseline survey. Surveys are self- administered on electronic tablets provided by the research staff (back up paper surveys will be used if tablets are not available or fail). All participants, regardless of the amount of curricular content completed, are eligible to take this survey; participants are asked to complete the end of program survey later if they miss the last session.

Emailed/text survey option: Participants who cannot attend the study site or other community site (e.g., due to lack of transportation, neighborhood barriers) for EOP survey administration will be offered the option to take the survey via email or a texted link on an internet-capable device (e.g., computer, smartphone). The RA will confirm via phone that the participant is OK to take the survey. The link will be specific to the email address that the young person provides and will only allow the survey to be taken once. Using REDCap's anonymous survey feature, we can create an individualized link to be sent to each participant's email or phone, and confirm if their survey was completed, but we cannot determine which survey data corresponds to that participant (i.e., remains anonymous). Phone call option: participants can also opt to complete the survey during a phone call with a research assistant, who reads aloud the questions and the participant responds; the research assistant enters the answers directly into the online survey tool.

Alternate contact information: We will also use the alternate contact information provided by youth upon study enrollment to reach them for follow-up surveys. This may include, but is not limited to, phone numbers or email addresses for parents, caregivers, other family members, and close friends. We then ask these contacts to facilitate us reaching the participant. Community site partners from the program are also contacted to ask for retention assistance.

Interviews: At or after the EOP survey, some youth will be invited to participate in a confidential interview about their experiences receiving the control or intervention, their feedback about the relevance of the program, and additional input about the impact of the program on themselves and their peers. The interviews will be digitally recorded, transcribed, and the audio files destroyed once the transcription has been checked for accuracy and all identifying information removed.

Data Management

Baseline and follow-up survey participation coincide with the beginning of the intervention and end of the program (EOP). All sites conduct web-based surveys (back up paper surveys are used as needed) on tablets using REDCap, an online data management and survey system. Youth provide detailed contact information at baseline to facilitate follow up. Contact information is confirmed again at sessions following the baseline survey. Responses to the anonymous web-based secure survey are entered by the youth participants themselves on an electronic tablet; no data are stored on the computers themselves.

Only research staff who have been added to the project can access this online database. Data are downloaded and stored on a password-protected share drive that can only be accessed by users with the appropriate permissions. No names are connected to the survey data as each participant creates their own secret code as described above. The only study documents that contain unique personal identifiers are contact forms and the contact list of participants (youth and prevention educators) that are kept to assist with re-contacting participants for follow up surveys. Contact forms are stored in a secure file drawer inside the locked office of the PI whenever not in use. Contact forms are stored separately from any survey data collected in this study (the survey data are collected via computer and immediately housed in a password-protected secure database). The names of participants are kept in encrypted files on a password-protected server behind the UPMC firewall.

